2.5 Development of predictive biomarkers

Baseline and early dynamic changes in qHBsAg, ELISPOT and NK cell parameters will be used alongside clinical and laboratory analyses to construct prognostic models for the prediction of HBsAg loss.

[figure not shown]
3 STUDY DESIGN

3.1 Pilot Phase

A pilot phase will be conducted at the beginning of the trial. This will consist of 50 patients recruited across 4 sites. Milestones within the pilot are based on numbers of patients recruited as well as safety aspects/numbers of exaggerated flares as shown in the flow diagram below. The pilot phase will be conducted according to the same protocol as the main trial and the pilot phase patients will count towards the overall trial sample size. Exaggerated flares are defined in Section 6.4 (i).

The milestones for the pilot phase are as follows:

- If the pilot phase fails to recruit 40 patients in 4 months then NIHR-EME will discontinue the study.
- If more than 40% of patients in either arm of the trial experience exaggerated flares by the end of the pilot phase then that arm will be discontinued. If this occurs in the interferon arm then the interferon arm will be modified to a control and combined interferon treatment protocol in which pegylated interferon is added to the nucleos(t)ide analogue for 16 weeks prior to cessation of therapy rather than leaving a gap between nucleos(t)ide analogues withdrawal and pegylated interferon treatment (and compared to the control arm still) see Figure 2. If this occurs in the control arm then the control arm will be switched to the interferon and combined interferon treatment protocol (and compared against the standard interferon arm) see Figure 3.
- If more than 60% of patients in the pilot experience exaggerated flares the trial will be discontinued.
- If more than 40% of patients in both arms experience exaggerated flare by the end of the pilot phase then the trial will be terminated if the DMEC and TSC recommend so.

A safety assessment will be made by the TSC and DMEC when all pilot patients will have completed initial screening, therapy gap and two months of interferon therapy. The trial will be assessed against the above milestones and a decision on the continuation of the trial made.

NUC-B	PROTOCOL Version 2.0 12 th Aug 2016	Sponsor Imperial College	
		impenal College	

3.2 Design

The main trial for NUC-B will be performed in at least 10 sites in England. It is a randomised, open-label, multicentre trial comparing nucleoside / nucleotide analogue withdrawal against nucleoside/ nucleotide analogue withdrawal followed by a 16 week course of pegylated interferon in HBeAg-negative chronic hepatitis B virus infected patients. Patients will be followed for 3 years after randomisation.

3.3 Treatment regimens

Table 1: Summary of treatment groups

Treatment Strategy	Number of subjects	Month 1	Month 2 - 5	Month 6 – 36
A: Withdrawal	120 (25 from pilot)	Withdraw nucleos(t)ide analogues	Follow up	Follow up
B: Interferon	120 (25 from pilot)	Withdraw nucleos(t)ide analogues	Pegylated interferon α2a 180 mcg s.c. o.w.	Follow up
Total number of subjects	240			 

Figure 1: Study flow chart

[figure not shown]

Figure 2: Control and combined interferon treatment Protocol (if more than 40% of patients in the original interferon arm of the pilot phase experience exaggerated flares by the end of the pilot phase)

[figure not shown]
[figure not shown]

Figure 3: Interferon and combined interferon treatment Protocol (if more than 40% of patients in the original control/treatment withdrawal arm of the pilot phase experience exaggerated flares by the end of the pilot phase)

4 PARTICIPANT ENTRY

4.1 Study population

Subjects for the trial will be recruited from hepatology or hepatitis specialist clinics where appropriate patients are already being monitored on treatment with nucleos(t)ide analogues. By definition these patients are strongly adherent with clinic appointments and antiviral drugs. Patients will be given a patient information sheet and invited to an appointment at least one week later.

The trial will be open to patients with HBeAg negative chronic HBV infection who have been treated with nucleos(t)ide analogues for a minimum of three years with HBV DNA < 400 IU/ml for a minimum of two years. After screening all patients will be monitored for 4 - 12 weeks to confirm they continue to meet the inclusion criteria as listed below.

(i) Inclusion criteria

- Age ≥ 18
- Chronic HBV infection
- HBeAg negative
- Nucleos(t)ide analogues treatment for ≥3 years
- HBV DNA < 400 IU/mI ≥2 years
- Informed consent

(ii) Exclusion criteria

- Cirrhosis at any time
- HBeAg to anti-HBe seroconversion within the last 3 years
- Interferon use in the last 3 years
- Contraindications to interferon use
- Participation in HBV-specific therapeutic vaccine studies within 12 months
- HCV, HDV or HIV co-infection
- Immunosuppressant use
- Contraindications to interferon use including:

- The presence of, or history of severe psychiatric condition, particularly severe depression, suicidal ideation or suicidal attempt
- Presence of or history of psoriasis
- Platelet count < 90000/mm³
- Absolute Neutrophil count < 1500/mm³
- Uncontrolled thyroid function
- Pregnancy or breastfeeding
- Women of child-bearing potential not using an effective method of contraception
- Men not using an effective method of contraception
- Clinically significant comorbidities that, in the opinion of the investigator, render the patient unsuitable.

5 PROCEDURES AND MEASUREMENTS

The trial will be open label meaning that both patients and their medical staff will know to which arm of the trial they are randomised. All patients in the trial will discontinue nucleos(t)ide analogues at baseline with the exception of the interferon arm in the alternative protocol (see Figures 2 and 3).

Occurrence of flares which require recommencement of nucleos(t)ide analogues will be an important measure of safety and efficacy in this trial and will therefore not be counted as a withdrawal from the study. Based on the previous studies of treatment cessation it is reasonable to expect up to 45% of patients to require retreatment.

A. Control arm

Patients randomised to the control arm will discontinue their nucleos(t)ide analogue treatment at baseline. They will be followed up until 3 years after randomisation.

B. Interferon arm

Patients randomised to the Interferon arm will discontinue their nucleos(t)ide analogue treatment at randomisation. No treatment will be given for 4 weeks and then they will commence pegylated interferon 180 mcg s.c. o.w α 2a and will continue taking weekly interferon for a total of 16 weeks. They will subsequently discontinue all antiviral medications. They will be followed up until 3 years after randomisation.

Although pegylated interferon has a long list of side effects which may be both unpleasant for the patients and potentially harmful, poor adherence to treatment is not anticipated. All the centres in this study are experienced in the use of pegylated interferon for the treatment of both HBV and HCV infection and invariably achieve adherence rates over 95%.

Control and combined interferon treatment Protocol – see Figure 2

By the end of the pilot phase, if more than 40% of patients in the interferon arm experience exaggerated flares then the arm will be modified to a control and combined interferon treatment protocol in which pegylated interferon is added to the nucleos(t)ide analogue for 16 weeks from randomisation and prior to cessation of therapy rather than leaving a gap between nucleos(t)ide analogues withdrawal and pegylated interferon treatment (and compared to the control arm still). They will subsequently discontinue all antiviral medications after the 16 weeks. They will be followed up until 3 years after randomisation.

Interferon and combined interferon treatment Protocol – see Figure 3

NUC-B PROTOCOL Version 2.0 12 th Aug 2016	Sponsor Imperial College
--	-----------------------------

By the end of the pilot phase, if more than 40% of patients in the control arm experience exaggerated flares then the control arm will be modified to the interferon and combined interferon treatment protocol in which pegylated interferon is added to the nucleos(t)ide analogue for 16 weeks from randomisation and prior to cessation of therapy. This will be compared against the standard interferon arm (used in the pilot phase). They will subsequently discontinue all antiviral medications. They will be followed up until 3 years after randomisation.

5.1 Screening and pre-randomisation evaluations

Written informed consent will be obtained before the subject undergoes any screening procedures as described in section 9.9.

All patients will have blood samples taken which will be processed and stored for later measurement of qHBsAg, ELISPOT assays and NK cell function.

Patients who consent to liver biopsy (estimated to be around 20 in number) will have a liver biopsy between screening and baseline with histological measurement of fibrosis, necroinflammatory scores and number of infected cells using immunohistochemistry for HBcAg and HBsAg. Biopsy tissue will be used to measure the level of cccDNA and to extract lymphoid cells for immunological phenotyping.

A Fibroscan (or ARFI) measurement will be made at baseline to confirm that cirrhosis is not present.

An ultrasound of the liver will be performed at baseline to exclude the presence of hepatocellular carcinoma.

5.2 Randomisation

Patients will be electronically randomised using the InForm eCRF online custom built database to the two management arms in equal proportions using variable block sizes. Randomisation will be stratified by gender and by HBsAg titre at baseline (< or \ge 2000 IU/mI) as this is the strongest predictor of clinical outcome in interferon based treatment and was found to be a predictor of outcome in the Hadziyannis study.

5.3 Visit Schedules Control Arm

Control A	,,,,											1	1
Visit number	1	2	3	4	5	6	7	8	9	10	11	12	13
Week	-4	0	4	8	12	16	24	32	52	78	104	130	156
Control Group	Screening ²	Baseline	Post week 4	Post week 8	Post week 12	Post week 16	Post week 24	Post month 8	Post month 12	Post Month 18	Post month 24	Post month 30	Post month 36
Consent	Х												
Demographic data	х												
Inclusion / Exclusion		Х											
Randomisation		Х											
Medical history	Х												
Vital signs	х	Х	Х	Х	Х	х	Х	х	Х	Х	Х	х	Х
Physical examination	х								Х		Х		х
Liver biopsy ¹	х												
USS/Fibroscan	х												
HBV Genotyping			Х										
qHBsAg	х												
HBsAg		Х	Х				Х		Х		Х		Х
HBV DNA	х	Х	Х	Х	Х	Х	Х	Х	Х	Х	Х	х	Х
LFTs	Х	Х	Х	Х	Х	Х	Х	Х	Х	Х	Х	х	х
Thyroid function	х												
Electrolytes & creatinine	х												
Prothrombin time	х	Х	Х	Х	Х	Х	Х	Х	Х	Х	Х	Х	Х
FBC	Х		Х				Х	Х	Х	Х	Х	х	х
PBMC collection (for immunology assays)		Х	Х				Х		Х		Х		х
Plasma/serum storage (for virology)		Х	х				Х		Х		Х		х
Adverse events		Х	Х	Х	Х	х	Х	Х	Х	Х	Х	х	х
Concomitant medications	х	Х	Х	Х	х	х	Х	х	Х	Х	Х	х	Х
Pregnancy test		Х											

Liver biopsy to be performed between screening and baseline in a sub-set of ~20 patients, 2. Baseline to occurs 4 – 12 weeks after initial screening

PROTOCOL Version 2.0 12th Aug 2016

Sponsor Imperial College

Interferon arm

Visit number	1	2	3	4	5	6	7	8	9	10	11	12	13	14	15	16
Week	-4	0	4	6	8	12	16	20	24	32	42	52	78	104	130	156
Interferon Group	Screening ²	Baseline	Gap week 4	IFN week 2	IFN week 4	IFN week 8	IFN week 12	IFN week 16	Post IFN week 4	Post IFN week 12	Post IFN week 22	Post randomisation month 12	Post randomisation Month 18	Post randomisation month 24	Post randomisation month 30	Post randomisation month 36
Consent	х															
Demographic data	х															
Inclusion / Exclusion		х														
Randomisation		х														
Medical history	х															
Vital signs	х	х	х	х	х	х	х	х	х	х	х	Х	Х	Х	Х	Х
Physical examination	х											Х		Х		Х
Liver biopsy ¹	х															
Ultrasound/Fibroscan	Х															
HBV Genotyping			х													
qHBsAg	х															
HBsAg		х	Х						х			Х		Х		Х
HBV DNA	х	х	х	х	х	х	х	х	х	х	х	Х	Х	Х	Х	Х
LFTs	х	х	х	х	х	х	х	х	х	х	х	х	Х	Х	Х	Х
Thyroid function	х				х			х		х						
Electrolytes & creatinine	Х		Х			Х		Х		Х		Х				
Prothrombin time	х	х	х	х	х	х	х	х	х	х	х	Х	Х	Х	Х	Х
FBC	х		Х	Х	Х	Х	Х	Х	Х		Х	х		Х		Х
PBMC collection (for immunology assays)		Х	х					Х	Х			х		Х		Х
Plasma/serum storage (for virology)		х	х					Х	Х			х		Х		Х
Adverse events		х	Х	х	Х	х	Х	Х	Х	Х	х	Х	Х	Х	Х	Х
Concomitant medications	х	Х	х	Х	Х	Х	Х	Х	Х	Х	Х	х	х	Х	Х	Х
Pregnancy test		Х	Х													

Liver biopsy to be performed between screening and baseline in a sub-set of ~20 patients, 2. Baseline to occurs 4 – 12 weeks after initial screening

PROTOCOL Version 2.0 12th Aug 2016

Sponsor Imperial College

Alternative Protocol Interferon Arm

Visit number	1	2	3	4	5	6	7	8	9	10	11	12	13	14	15	16
Week	-4	0	2	4	8	12	16	20	24	28	40	52	78	104	130	156
Interferon Group	Screening ²	Baseline	IFN week 2	IFN week 4	IFN week 8	IFN week 12	IFN week 16	Post IFN week 4	Post IFN week 8	Post IFN week 12	Post IFN week 24	Post randomisation month 12	Post randomisation Month 18	Post randomisation month 24	Post randomisation month 30	Post randomisation month 36
Consent	Х															
Demographic data	х															
Inclusion / Exclusion		х														
Randomisation		х														
Medical history	х															
Vital signs	х	х	х	х	х	х	х	х	х	х	х	Х	Х	Х	Х	Х
Physical examination	х											Х		Х		Х
Liver biopsy ¹	х															
Ultrasound/Fibroscan	х															
HBV Genotyping								х								
qHBsAg	х															
HBsAg		х		х				х				Х		Х		Х
HBV DNA	х	х	х	х	х	х	х	х	х	х	х	Х	Х	Х	Х	Х
LFTs	х	х	х	х	х	х	х	х	х	х	х	Х	Х	Х	Х	Х
Thyroid function	х			Х			х				х					
Electrolytes & creatinine	Х				Х		Х			Х		х				
Prothrombin time	х	х	х	Х	х	х	х	Х	х	х	х	Х	Х	Х	Х	Х
FBC	Х		Х	Х	Х	Х	Х	Х			х	х		Х		Х
PBMC collection (for immunology assays)		х						Х		х		х		Х		Х
Plasma/serum storage (for virology)		Х						Х		Х		х		Х		Х
Adverse events		х	Х	х	х	х	х	Х	х	х	х	Х	Х	Х	Х	Х
Concomitant medications	Х	Х	Х	Х	Х	х	Х	Х	х	Х	х	х	х	Х	Х	Х
Pregnancy test		х														

1. Liver biopsy to be performed between screening and baseline in a sub-set of ~20 patients, 2. Baseline to occurs 4 – 12 weeks after initial screening

Additional visits may be made during interferon therapy to support or instruct patients but these will not be considered as study visits and will not be recorded in the study CRF.

Additional visits may be made at the discretion of the investigator for safety monitoring if hepatitis flares occur or for other safety reasons. These will be recorded in the unscheduled visit form.

Visit windows/tole	erance.

Arm	Visit	Tolerance
Interferon Arm	2	2 weeks – 3 months
(including	3-12	+/- 3 days
alternative	13-16	+/- 10 days
interferon arms)		
Withdrawal	2	2 weeks – 3 months
(control arm)	3-8	+/- 3 days
	9 - 13	+/- 10 days

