OBJECTIVES The aim of this trial is to explore whether finite treatment with nucleos(t)ide analogues is feasible in patients with HBeAg (Hepatitis B 'e' antigen) negative chronic HBV (Hepatitis B Virus) infection. This aim encompasses an exploration of therapeutic strategies to achieve HBsAg (Hepatitis B surface antigen) loss; specifically the trial is designed to evaluate whether a short course of pegylated interferon after nucleos(t)ide analogue withdrawal stimulates antiviral immunity sufficiently to increase the rate of HBsAg loss.

Loss of HBsAg, the most important serological marker of HBV infection, is widely accepted (including by the Food and Drug Administration (FDA) & European Medicines Agency (EMA)) as an indication of cure in chronic HBV infection and is associated with absence of long term sequelae in non-cirrhotic patients. HBsAg is a cheap and universally available serum marker. Loss of HBsAg allows patients to be discharged from follow-up with consequent health-economic benefits.

DESIGN NUC-B will be a multicentre, randomised, open label trial comparing two management strategies to promote HBsAg loss in patients with HBeAg negative chronic HBV infection.

SAMPLE SIZE A trial with 90% power to detect a difference in HBsAg loss between these groups at the P < 0.05 threshold would require 109 subjects in each arm. Allowing for ~10% withdrawal / dropout in each arm we will aim to recruit 120 subjects to each arm; 240 patients in total.

ELIGIBILITY CRITERIA Adult patients aged 18 and above with chronic HBeAg negative hepatitis B virus infection on nucleos(t)ide analogues treatment for 3 years or more.

TREATMENT/MAIN STUDY PROCEDURES

Registered patients will be followed for 4 – 12 weeks between initial screening and randomisation in order to collect data on quantitative HBsAg levels and anti-viral immune responses. During this period a sub-set of consenting patients will receive a liver biopsy for analysis of fibrosis and necroinflammatory scores, measurement of cccDNA and analysis of T cell and NK cell infiltrates.

If the patient remains eligible, electronic randomisation will then allocate subjects to two arms:

1. Control arm

Patients randomised to the Treatment Withdrawal arm will discontinue their nucleos(t)ide analogue treatment at baseline.

2. Interferon arm

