5.5 Follow-up

In the control arm visits 3-6 will be used to monitor safety. In the Interferon arm visits 4 - 8 will be used to monitor and manage the side effects of interferon therapy.

Biological samples will be taken according to the relevant visit schedule in Section 5.3.

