5.7 Clinical investigations

Physical examination

A brief clinical examination will be conducted to eliminate features associated with decompensated cirrhosis and to measure vital signs. Vital signs will be measured at every visit, including the following: systolic and diastolic blood pressure, heart rate and temperature.

Ophthalmology examination

All patients in the interferon arm will have a baseline eye examination.

Concomitant medications

Records of all prescribed and over the counter medications will be collected at each visit.

Medical History

A history of significant previous illnesses and ongoing co-morbidities will be collected.

Fibroscan (or ARFI)

A measurement will be made at the screening visit to confirm that cirrhosis is not present.

Ultrasound

An ultrasound of the liver will be performed at the screening visit to exclude the presence of hepatocellular carcinoma.

Pregnancy test

A pregnancy test will be performed at the baseline visit for all females who are not considered to be using adequate contraception. In the interferon arm an additional pregnancy test will be performed at the visit before interferon treatment commences to ensure that patients are not pregnant before commencing treatment. Patients will be asked to use adequate contraception whilst on interferon to prevent pregnancy or for male participants to prevent pregnancy in a female partner.

Adequate birth control methods are defined as those that can achieve a failure rate of less than 1% per year when used consistently and correctly. Examples include hormonal contraception, intra uterine device, bilateral tubal occlusion, vasectomised partner, sexual abstinence. Abstinence is only acceptable if it is true abstinence in line with the preferred and usual lifestyle of the patient. Periodic abstinence such as calendar, ovulation, post-ovulation, and declaration of abstinence for the duration of exposure to IMP and withdrawal are not acceptable methods of contraception.

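### In the contingent alternative interferon schedule no full blood count is marked at the first-dose visit, so the first two or three injections rest on a screening count 4 to 12 weeks old

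*Protocol*

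**What the plan says.** Protocol section 5.3 gives three visit tables: control, standard interferon, and the one headed "Alternative Protocol Interferon Arm". The third applies only if the pilot flare criterion in section 3.1 is met (more than 40% exaggerated flares in an arm).

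- **Start of interferon.** Section 5 states for both contingent designs that "pegylated interferon is added to the nucleos(t)ide analogue for 16 weeks from randomisation and prior to cessation of therapy". The first dose therefore belongs to visit 2, week 0. The table agrees, since its week-2 column is labelled as the second interferon week.
- **FBC marks in the alternative table.** Visits 1, 3 to 8, 11, 12, 14 and 16. Visit 2 is blank.
- **Interval from screening.** The table footnote reads "Baseline to occurs 4 – 12 weeks after initial screening". The visit-window table allows 2 weeks to 3 months for visit 2.
- **Count limits.** Section 4.1 lists "Platelet count < 90000/mm³" and "Absolute Neutrophil count < 1500/mm³" among the contraindications to interferon. Section 6.3 reduces or stops the dose on the same two counts.
- **Eligibility at baseline.** The inclusion/exclusion row is marked at visit 2, and the Trial Summary says "If the patient remains eligible, electronic randomisation will then allocate subjects to two arms".
- **A contraindication that is rechecked.** For pregnancy in the interferon arm, section 5.7 says "an additional pregnancy test will be performed at the visit before interferon treatment commences to ensure that patients are not pregnant before commencing treatment". The alternative table marks that test at visit 2.

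**The concern.** Two blood-count limits decide whether a patient may receive interferon at all, and the same counts govern dose reduction and stopping. In the alternative arm the protocol schedules no count at the visit where the first injection is given. A patient whose neutrophils or platelets fell below the limit after screening would not be picked up by a scheduled test until about two weeks into treatment. With no week-0 value, a low count at week 2 also could not be separated from a fall that predated dosing.

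What is at stake is patient safety in a contingent arm. Sample size, power and the primary analysis are unaffected.

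**Working it through.** **Step 1. Line up the FBC marks by interferon time.** Each interferon table has 16 FBC cells for 16 visits, so no column has been lost or shifted.

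| Time point | Standard interferon table | Alternative table |
|---|---|---|
| Screening | visit 1, marked | visit 1, marked |
| Randomisation (week 0) | visit 2, blank | visit 2, blank |
| First-dose visit | visit 3 (week 4), marked | visit 2 (week 0), **blank** |
| Interferon weeks 2, 4, 8, 12, 16 | visits 4 to 8, marked | visits 3 to 7, marked |
| 4 weeks after interferon | visit 9, marked | visit 8, marked |
| 22 or 24 weeks after interferon | visit 11, marked | visit 11, marked |
| Months 12, 24, 36 | visits 12, 14, 16, marked | visits 12, 14, 16, marked |

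The first-dose visit is the only point where the two rows differ in substance. The control table has FBC at visits 1, 3 and 7 to 13, so it too is blank at baseline and marked at week 4.

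**Step 2. Look for a pre-dose count elsewhere.** Section 5.5 refers sampling to the section 5.3 tables. Sections 5.1 and 5.6(i) add no baseline FBC. Section 5.4 describes the supervised first injection and mentions no count.

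**Step 3. Age of the last scheduled count at first dose.**
- Alternative arm: 4 to 12 weeks by the footnote, or 2 weeks to 3 months by the visit-window table.
- Standard arm: 0 weeks, because FBC is marked at the first-dose visit.

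**Step 4. Injections given before the next count.** Take the first dose as day 0, with weekly injections on days 0, 7 and 14. Visit 3 is day 14 ± 3, that is day 11 to day 17.
- Visit on day 11: injections on days 0 and 7, so 2.
- Visit on day 14 with blood taken before that day's injection: 2.
- Visit on day 17: injections on days 0, 7 and 14, so 3.

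**Step 5. Gap between the two scheduled counts, by the footnote.**
- Nominal: 4 + 2 = 6 weeks to 12 + 2 = 14 weeks.
- With the ± 3 days: (28 + 11)/7 = 5.6 weeks to (84 + 17)/7 = 14.4 weeks.

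**Step 6. Patients exposed.** Section 3.3, Table 1 gives 120 per arm with 25 from the pilot: 120 − 25 = 95, which agrees with (240 − 50)/2 = 95. This is a ceiling. The pilot decision waits until all pilot patients have had two months of interferon, and the protocol does not say that recruitment pauses meanwhile. Anyone randomised in that interval would be on the original regimen. If the trigger is not met, the number is zero.

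**Step 7. With FBC marked at visit 2,** the age of the last count at first dose falls from 4 to 12 weeks to 0 weeks.

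**The case against.** The strongest reply is that nothing in the protocol is contradicted. No section asks for an FBC before the first dose. FBC is blank at baseline in all three tables, so the general convention is to apply the count limits from the screening sample. Thyroid function is handled the same way: uncontrolled thyroid function is a listed contraindication, yet the standard interferon table marks the test at visits 1, 5, 8 and 10, with no recheck before the week-4 first dose. The Trial Summary's requirement that the patient still be eligible names no test, and the monitoring described in section 4.1 refers to the inclusion criteria, whereas the count limits are exclusion criteria. All of this stands.

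A reader might go further and infer that the standard visit-3 FBC was a deliberate pre-dose check, lost when the gap visit was removed. The table in step 1 makes that plausible but does not establish it. Control patients also have a week-4 FBC, and section 5.5 says "In the control arm visits 3-6 will be used to monitor safety", so the standard mark may be ordinary monitoring. The protocol also does not say that the standard-arm result must be reviewed before injection. What survives is the fact, whatever its purpose: standard-arm patients have a count at first dose and alternative-arm patients do not.

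Nor do the documents support inferring that patients with contraindicated counts will be dosed in any number. They give no rate of new low counts between screening and baseline. Patients have passed both limits at screening, remain on established nucleos(t)ide treatment, and are free of cirrhosis and immunosuppressants. FBC follows at week 2 with dose rules attached, and investigators may add safety visits. These facts keep the point minor. Discretionary visits do not, however, replace a scheduled check on a listed contraindication.

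**Conclusion.** The gap is real and small. In the alternative schedule the first two or three injections are given on a neutrophil and platelet count 4 to 12 weeks old, while the standard arm has a count at its first-dose visit. It should be treated as an inexpensive improvement to a contingent safety schedule. It is not a breach of any stated rule and has no bearing on the trial's statistical results.

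The conclusion assumes that the first injection is given on the day of visit 2, as the week labels imply, and that sites follow the tables as printed. At most about 95 patients are exposed, and none if the pilot trigger is not met. How many of them would have a newly low count cannot be estimated from the protocol, but it is likely to be few.

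**What to change.** In the alternative table of section 5.3, mark FBC at visit 2, using blood already drawn there for liver function, prothrombin time and HBV DNA. Add a short rule: the neutrophil and platelet results are reviewed before the first injection; if neutrophils are below 1500/mm³ or platelets below 90000/mm³, the injection is held and the count repeated; the patient stays in follow-up and in the intention-to-treat set. The last clause is needed because visit 2 is also the randomisation visit and section 8.2 defines that set as all randomised subjects. A low result must not become a post-randomisation exclusion in one arm only.

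An alternative is to take the FBC shortly before randomisation in both arms, so that eligibility itself rests on a current count. This treats the arms alike and avoids randomising a patient who cannot start interferon.

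Cost of the first option: one table mark, a brief rule, at most about 95 routine local tests, and a possible short delay to the first injection. The pre-randomisation option needs up to 2 × 95 = 190 tests and a result in hand before allocation.
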